3.1 Study design

The CABGpreHAB feasibility study is designed as a randomized pilot study, aiming to assess the feasibility of a multimodal prehabilitation intervention plus usual care versus usual care alone in patients awaiting elective CABG surgery. It is an investigator-initiated study designed as an open-label, single-center randomized controlled feasibility study (allocation ratio 1:1) with blinded outcome assessment, designed to assess the method proposed for use in a larger RCT. This protocol follows guidance from Standard Protocol Items: Recommendations for Interventional Trials (SPIRIT).⁶⁰ The CABGpreHAB study will be registered at www.ClinicalTrials.gov before initiation.

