3.4 Blinding

Due to the nature and conditions of prehabilitation, the interventions are open, making it impossible to blind the interventions to the staff and patients.⁶¹ However, all physical testing, data collection, and administration will be conducted by blinded staff. Statistical analysis of outcomes and the conclusions derived from these analyses will also be performed in a blinded manner. The study results will be analyzed by an independent statistician, and the research group will interpret the results. The conclusions will be prepared in two versions before the allocation code is broken, with each version assuming alternately that one arm is the intervention: one version will assume that arm A is the intervention, and the other will assume that arm B is the intervention.

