6.2.1 Exercise intervention

During the initial assessment patients will be taught how to perform the exercises to complete at home during the intervention period. The exercise intervention is supervised by skilled physiotherapists and delivered via Infinity Connect app and a webcam⁷² at Rigshospitalet to a group of approximately 4–8 patients who exercise at home and communicate via a tablet. Each session is 60 min, i.e., 40 min of exercise and 20 min of patient education, three times per week for the prehabilitation period. The exercises used in the program are identified and selected amongst exercises used in previous exercise intervention studies and involves larger muscle groups with 50/50% exercises for upper and lower extremities, respectively.⁷³ The exercises are executed in four sets to achieve peripheral muscle fatigue and secondary dyspnea/breathlessness. Each set is carried out in a predefined period of 20 to 40 s with a maximum number of repetitions performed, i.e., 8 to 25 repetitions depending on the patients exercise capacity and motivation, but with the aim of 12 to 20 repetitions.^{73,74} In practice the training intensity is determined by using the self-rated Borg Scale, moderate intensity RPE 11-15, 50-60% VO₂peak.⁷⁴

The first week serve as a familiarization phase with the purpose to adapt to exercising, adjusting, and optimizing load and to avoid musculoskeletal overload injuries. Monitoring physical activity and providing motivation through phone calls weekly will be enhanced by incorporating a novel accelerometer system, offering activity level feedback (SENS innovation)⁷⁵ to guide healthcare staff. Participants in the intervention will be instructed to perform daily exercise tasks such as brisk walking and sit-stand exercises. Additionally, motivational phone calls will be made to participants in the intervention group, while healthcare staff will receive feedback on these patients, aiding to guide them in achieving their activity goals. Patients will also be asked to complete a diary describing physical activity outside the programmed session, included in a patient booklet. All study participants will wear the accelerometer from the screening phase until the day preceding the procedure, and again postoperatively until the day of discharge and for 30 days

thereafter.^{76,77} The technology platform provided to the patients includes a tablet and an accelerometer device to facilitate exercise training sessions and data collection.

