8.1 Data from questionnaires

The questionnaires are self-administrated and will be completed electronically in REDCap a web-based data capture tool¹⁰³ which meets the data legislation for logging. The study participant will receive an email with link to a website through which questionnaires can be completed. The e-mail contains a login and password for the trial participant's access. If patients do not complete the questionnaire electronically, the paper questionnaires will be handed out to the patient, and independent study personal then enters the responses into REDCap. Participants will complete the questionnaires at all three time points: baseline, the day before CABG surgery after the intervention, and 30 days post-surgery. The filled-out questionnaires typed in REDCap and responses will be stored in a secure folder with limited access ("lovbeskyttet mappe").

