8.2 Data from patient records

Preoperative relevant information, including patient name and age as well as details about the patient's heart diagnosis and medical status (such as Euroscore II, LVEF, and NYHA class), will be reviewed from the patient record (SP) without consent by the responsible heart surgeon to inform the study about eligibility of patients referred to elective CABG surgery. Additionally, and with consent, postoperative complications, such as infections and arrhythmias, along with any adverse events occurring during the intervention period, will be documented from the patient record. Information on the length of stay (both ICU-LOS and overall, LOS) and the number of days alive out of the hospital within 30 days will be calculated using data from both the patient record and Danish registers. Data will be retrieved from the national electronic record system (E-journal) by an electronic healthcare software (Epic, Madison, WI, USA), which secures a complete enrolment and follow-up as the recording is a requirement for economic reimbursement. All data is processed and stored confidentially, and personal data will always be handled in accordance with the Danish Data Protection Act and the General Data Protection Regulation. Data are stored pseudo-anonymously in a separate approved and secure database (Capital Region REDCap), which only the doctors, research assistants and project nurses of the study will access using person-specific log-in and password. An anonymous trial number are used as patient identification in the REDCap database. The key linking the study-id with the personal id is kept separately from the study data with limited access controlled by the study investigator or designee. Authority and obligations are documented in the log of delegation of responsibility in the trial. The patient's records will be reviewed by study related personnel to assess clinical and safety endpoints. The informed consent gives the investigator and possibly control authority direct access to data from the patient's journal. These are used to view information on the participant's medical condition necessary for the conduct of the study and for self-control, quality control and monitoring. The patient is informed about this and gives informed consent to this when entering the study. If a potential participant declines to participate in the project, we will request permission to collect information regarding their age, gender and current medical status pertinent to their admission for CABG surgery and only if a written informed consent is obtained.

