9.1 Statistical methods

Data analysis will be limited to descriptive summary statistics of the proposed endpoints, and calculation of feasibility measures, enrollment rates and dropout rates within a period. The feasibility analysis will be based on the components of process, resources, management, and scientific approach.⁵⁸ Process: number of eligible patients for enrollment; Successful recruitment rate, rate of adherence to the interventions at each time point; Rate of loss to follow up; Rates of completed questionnaires; Understanding of the questionnaires. Resources: Time to screen and consent patients, Time to conduct baseline and follow-ups; Identification of any challenges related to randomization or data collection; Identification of potential barriers of the preoperative programme. Management: Identification of any challenges related to randomization or data collection; Identification of potential barriers for the intervention. Scientific approach: Estimates of improvement in patient-reported outcomes compared to usual care, patients' response to topics and content in the programme and identification of potentially patient safety issues. As recommended for the analysis of pilot studies⁵⁸ descriptive statistics will be presented as mean and standard deviations (SD) for continuous variables and frequencies and percentages for categorial variables at baseline and follow-ups. Collected data on patient characteristics will be presented in tables. Continuous variables will be displayed as mean (SD), while categorical variables will be presented as number (n) and percentage (%). Descriptive statistics will be used to answer the primary study parameter of feasibility. Feasibility will be presented in tables and based on participation rate (n, %), reasons for nonparticipation (n, %, text), adherence to the prehabilitation program (%), dropout rates (%), reasons for dropout (n, %, text), adverse events (n, %, text). The secondary aim is to evaluate the patients' responses over time in terms of physical activity, muscle strength, functional capacity, body composition, quality of life and symptoms of depression, and anxiety. A repeated measurements analysis will be used to analyze changes over time in continuous variables. *P*- values <0.05 will be considered statistically significant.

10. Ethics

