10.3 Risks and benefits

The interventions are expected to cause limited risks, side effects and discomfort. Patients are expected to benefit from homebased prehabilitation due to multimodal preoperative preparation before CABG-surgery improving functional capacity, reducing symptoms of anxiety and depression. Individualized and optimized preoperative care through exercise, supportive nursing counselling will be performed by experienced project nurses, physiotherapists and physicians, and patients will not experience any kind of delays or complications related to the interventions or follow-up process due to participation in the project. Before commencing the exercise components of the prehabilitation program, a physiotherapist will assess the participants' physical capacity. Previous studies have demonstrated the safety of preoperative physical exercise programs involving mild intensity training in patients scheduled for CABG surgery.^{6,27,106,107} The physical training regimen will adhere to the established recommendations for physical exercise in patients awaiting CABG surgery, ensuring the safety and efficacy of the exercise program.^{108,109} Standard blood sampling, which may cause slight discomfort from the needle stick, is expected as part of the procedure.

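### The unqualified claim of blinded outcome assessment and blinded data collection (3.1, 3.4) does not fit the self-rated outcomes, the adherence and adverse-event data, or the project nurses' database access

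*Protocol*

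**What the plan says.** Section 3.1 presents the study as open-label "with blinded outcome assessment". Section 3.4 concedes that the nature of the programme rules out masking, "making it impossible to blind the interventions to the staff and patients", and then adds that "all physical testing, data collection, and administration will be conducted by blinded staff". It also provides for a blinded analysis, with conclusions drafted in two versions before the code is broken.

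Other sections describe how the data arise:

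- Section 8.1: "The questionnaires are self-administrated and will be completed electronically in REDCap". Independent personnel enter any paper forms.
- Table 1 in section 7.2 lists smoking and alcohol status as self-reported.
- Section 7.1 takes adherence from a patient logbook, the weekly calls and the accelerometer. Under safety, the physiotherapist notes undesirable effects around the tele-sessions or nurse calls.
- Section 8.2 describes the REDCap database as one "which only the doctors, research assistants and project nurses of the study will access using person-specific log-in and password".
- Section 10.3: "supportive nursing counselling will be performed by experienced project nurses". Sections 6.2.3 and 7.1 confirm that the project nurse is the patient's contact and telephone counsellor.
- Section 9.1 lists, under scientific approach, "Estimates of improvement in patient-reported outcomes compared to usual care".

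**The concern.** Blinded outcome assessment is a property that readers rely on when they judge an estimate from an open-label trial. In a self-rated questionnaire the patient is the assessor. A patient who knows that he or she received weekly nurse calls and supervised exercise may report less anxiety or better quality of life out of expectation or courtesy. Blinding the tester, the data-entry clerk or the statistician does not remove that.

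Section 2.2 asks whether the programme has an impact and says that the outcome data will inform the sample size of the future trial. If an optimistic patient-reported difference is carried forward under a blinded-assessment label, the planners of that trial will give it more weight than it deserves.

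**Working it through.** The protocol gives no figure to reproduce. The check compares the blinding statements with the sections on who rates, collects and sees each kind of data, and then counts.

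**1. Who produces each outcome**

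| Data | Source (section) | Is the blinding claim met? |
|---|---|---|
| 6MWT, sit-to-stand, hand grip, BIA | Staff-run tests (Table 1) | Yes, if done as 3.4 says |
| SF-12, HeartQoL, STAI, PHQ-4, PAM13 | Completed by the patient (8.1) | No: the rater knows the arm |
| Tobacco, alcohol | Patient self-report (Table 1) | No, for the same reason |
| Accelerometer | Device (Table 1) | Recording does not depend on a rater |
| Adherence | Logbook, weekly calls, accelerometer (7.1) | No: collected through programme delivery |
| Adverse events | Sessions and calls (7.1), also patient record (8.2) | No for the first route; not stated for the second |
| Complications, length of stay, DAOH30 | Records and registers (8.2, 8.3) | Possible; 8.2 does not say that the reviewer is blinded |

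**2. How much is self-rated**

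Secondary-outcome rows of Table 2 with a baseline mark and at least one later mark:

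- not self-rated: 6MWT, BIA, hand grip, sit-to-stand, accelerometer = 5
- self-rated: SF-12, HeartQoL, STAI, PHQ-4, PAM13, tobacco, alcohol = 7
- share: 7 / (5 + 7) = 7/12 = 58%

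The share depends on the denominator:

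- Rows marked at baseline, the day before surgery and day 30 (without BIA and hand grip): 7/10 = 70%.
- Repeated rows plus the blood-test row: 7/13 = 54%.
- All clinical rows with a mark after baseline. This adds complications, length of stay, DAOH30, rehabilitation participation and blood tests, counts rehabilitation participation as self-report, and leaves out the adverse-event row: 8/17 = 47%.

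Self-report is therefore a modest majority of the repeated measures, and about half of everything measured after baseline.

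**3. Who can see outcome data**

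Questionnaires are held in REDCap (8.1). REDCap access goes to doctors, research assistants and project nurses (8.2). Project nurses counsel intervention patients (6.2.3, 7.1, 10.3). Assuming that 8.1 and 8.2 describe the same database, staff who know the allocation because they deliver the programme can reach the outcome data. No restriction by role or by blinding is stated.

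**4. Where it bears on the results**

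The one between-arm clinical comparison that 9.1 names concerns patient-reported outcomes, which is the unblinded group in step 1. The criteria in 7.1 for going on to a larger trial concern participation and receipt of the intervention.

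**The case against.** The best defence is that nothing is hidden. Section 3.4 says openly that patients are unblinded, its next sentence is about staff, and section 8.1 says that questionnaires are self-administered. This stands: for the questionnaires, the fault lies in the unqualified phrase in 3.1 and not in a false statement in 3.4. It does not help with adherence and session-based adverse events, because 3.4 covers all data collection and these data are gathered by people who deliver the programme.

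On REDCap, log-ins are personal, responsibilities are kept in a delegation log, paper forms are entered independently, and form-level rights may be set elsewhere. A reader might infer that treating nurses rate or alter outcomes. The protocol does not say so; it only leaves the access open.

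A reader might also infer that feeding accelerometer data to staff ("healthcare staff will receive feedback on these patients, aiding to guide them in achieving their activity goals") biases that outcome. It does not show this. The feedback is part of the intervention, the device records whoever looks at the data, and more activity after coaching is an intervention effect. Nor does anything show that the research nurse who interviews patients the day before surgery also runs the physical tests.

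Finally, it is tempting to turn an expectation effect into an inflated false-positive rate. Section 9.1 restricts the analysis to descriptive summaries, apart from a repeated-measurements analysis of change over time. It specifies no between-arm test, and the documents give no size for such an effect, so no rate can be derived.

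**Conclusion.** The point holds as a correction to a stated design property. The blinding claim in 3.1 and 3.4 is broader than the design: 7 of 12 repeated secondary measures are unblinded self-report, adherence and part of the adverse-event data come through programme delivery, and programme nurses have database access without a stated limit.

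It would go too far to say that the blinding protects little beyond the physical tests. Record and register endpoints such as DAOH30 and length of stay, and the blood tests, depend little on blinding. The blinded analysis and the two-version conclusions also remain intact as a separate safeguard.

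The effect on the study is limited because the primary aim is feasibility. It falls on the exploratory patient-reported comparison and on how the full trial's planners read it. The size of any bias cannot be given from the documents. The conclusion rests on the row count above and on reading 8.1 and 8.2 as one database.

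**What to change.** - **3.1 and 3.4:** limit the blinding claim to the assessor-run physical tests (6MWT, sit-to-stand, hand grip, BIA), to extraction from records and registers if blinded staff do it, and to the analysis. State that self-reported outcomes, adherence and adverse-event collection are unblinded.
- **9.1:** label between-arm estimates of patient-reported outcomes as unblinded, and read them beside the blinded physical tests.
- **8.2:** set REDCap rights so that staff who deliver the programme cannot open or edit outcome forms, and say so.

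The cost is protocol wording and a rights setting, with no added visits or measurements. The downside is a less favourable blinding claim.

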3.5 Participant timeline

After the MDT conference eligible patients identified from the elective waiting list for CABG-surgery are invited to participate. When they have contended, they will be allocated to either CABGpreHAB plus usual care or usual care alone. The intervention will be launched immediately after inclusion in the study. At baseline a face-to-face introduction and counselling will take place at the preoperative clinic at the Department of Cardiothoracic surgery Rigshospitalet. There will be assessment at baseline, the day before surgery (ending of the intervention period) and on day 30 post surgery. All study participants will wear the accelerometer from the screening phase until the day preceding the procedure, and again postoperatively until the day of discharge and for 30 days thereafter as illustrated in **Figure 2**.

[figure not shown]

Figure 2. Graphical illustration of the study design

3.6 Sample size and power

As the primary aim of this study is to evaluate feasibility, there is no formal requirement for a formal power calculation.⁶² Sample sizes between 24 and 50 have been recommended.^{63,64} A sample size of 25 patients in each group was chosen as it seems reasonable to provide outcome data in a small sample, and at the same time a sample size large enough to investigate the additional aspects that are being assessed for feasibility⁶⁵ informing a future power calculation for a full-scale RCT.

4. Selection and allocation of participants

Following the MDT conference in the department of Heart and Lung Surgery, Rigshospitalet the responsible surgeon screen for eligibility by comparing patients' referral against the inclusion and exclusion criteria as described in this protocol section 4.1. If the patient is deemed eligible after screening, they will receive an invitation in e-Boks to be contacted for a brief information about the study. If they accept this invitation, the patient will be contacted by telephone by a responsible clinician in the project, and if the patient is interested to hear more, written information material about the study will be send by e-Boks or regular post. The patient will be informed that participating is voluntary, that they have the right to bring a bystander for the oral information, which will take place when they meet for the planned visit in the pre-clinic some days later. If patients haven't got the invitation about information in E-boks the responsible surgeon will introduce the study for eligible patients and present patients with the written information at the meeting in the pre-clinic. The oral information will be given with no external interruptions and will be given in a language easily understood without technical or value laden terms. The patient will receive a full explanation of the study design and study procedures, and information about usual care. This information interview is performed by the principal investigator or in her absence by a designated delegate. Consent to participation is given on the basis of written and oral information. Prior to consent, it must be ensured that a potential participant has been given sufficient time to consider his or her participation and minimum 24 hours. However, potential participants can sign earlier if they wish. An informed consent form must be signed and dated by the participant prior to participation in the trial. A copy of the form is provided to the participant. The principal investigator and her designated delegates can receive the signed consent form. When the written informed consent is received, the study specific procedures such as test, randomization and other study related procedures will take place.

Patients will be eligible if they comply with the inclusion criteria in line with previously used criteria.^{66,67} Exclusion criteria are listed below.

4.1 Inclusion criteria

- Planned to have elective isolated first-time CABG surgery.
- 18 years or older
- Two weeks or more prior to surgery
- Speaks and understands Danish.
- Gives written informed consent.

4.2 Exclusion criteria

- Patient with unstable angina pectoris and/ or MI during the last two weeks.
- Left main stem stenosis >50%
- Left ventricular ejection fraction < 35%
- Significant ventricular arrhythmia
- Orthopedic or neurologic preconditions precluding exercise training.
- Inability to attend the prehabilitation program due to physical limitations.
- Patients who have cognitive deficits that would disqualify prehabilitation.
- Severe heart failure, NYHA Class IV
- Lack of capacity to consent

